# Appendix 4 Prohibited Strong P-Glycoprotein Inhibitors and Strong CYP3A Inducers and Inhibitors

Prohibited Strong P-Glycoprotein Inhibitors		
Amiodarone	Indinavir	Ranolazine
Atorvastatin	Itraconazole	Reserpine
Boceprevir	Ketoconazole	Ritonavir
Bromocriptine	Linagliptin	Saquinavir
Captopril	Lopinavir and ritonavir	Simeprevir
Carvedilol	Lovastatin	Simvastatin
Cobicistat	Meperidine	Suvorexant
Conivaptan	Methadone	Tacrolimus
Cyclosporine	Nelfinavir	Tamoxifen
Diltiazem	Nicardipine	Telaprevir
Doxazosin	Pentazocine	Ticagrelor
Dronedarone	Progesterone	Verapamil
Felodipine	Quercetin	
Fluvastatin	Quinidine	

Prohibited Strong CYP3A Inhibitors	Prohibited Strong CYP3A Inducers
Indinavir	Efavirenz
Nelfinavir	Nevirapine
Ritonavir	Phenobarbital
Itraconazole	Phenytoin
Ketoconazole	Pioglitazone
Nefazodone	Rifabutin
Saquinavir	Rifampin
Suboxone	St. John's Wort
Carbamazepine	Troglitazone

# Appendix 5 Drugs That Prolong QT

Anticonvulsants	Fosphenytoin; Felbamate
Antihistamines	Azelastine, Clemastine
Anti-infectives	Amantadine, Clarithromycin, Chloroquine, Foscarnet, Erythromycin, Halofantrine, Mefloquine, Pentamidine, Sparfloxacin, Quinine, Trimethoprim-Sulfamethoxazole, Ketoconazole
Antineoplastics	Tamoxifen
Cardiovascular	
Antiarrhythmics	Amiodarone, Bretylium, Disopyramide, Flecainide, Ibutilide, Procainamide, Quinidine, Sotalol, Dofetilide
Calcium Channel Blockers	Bepridil, Israpidine, Nicardipine
Diuretics	Indapamide, Moexipril/ hydrochlorothiazide
Hormones	Octreotide, Vasopressin
Immunosuppressives	Tacrolimus
Migraine: Serotonin Receptor Agonists	Zolmitriptan, Naratriptan, Sumatriptan
Muscle Relaxants	Tizanidine
Narcotic Detoxification	Levomethadyl
Psycotherapeutics	
Antidepressants	Amitriptyline, Desipramine, Fluoxetine, Imipramine, Venlafaxine
Antipsychotics	Chlorpromazine, Haloperidol, Pimozide, Quetiapine, Risperidone, Thioridazine
Antianxiety	Doxepin
Antimanic	Lithium
Respiratory (Sympathomimetics)	Salmeterol
Sedative/Hypnotics	Chloral hydrate

Note: List not exhaustive

## LIST OF ABBREVIATIONS

ACM	All-cause mortality
AE	Adverse event
ALP	Alkaline phosphatase
ALT	Alanine aminotransferase
AST	Aspartate aminotransferase
ATC	Anatomical Therapeutic Chemical
ATS	American Thoracic Society
BAL	Bronchoalveolar lavage
BUN	Blood urea nitrogen
C	Celsius
CABP	Community-acquired bacterial pneumonia
CE	Clinically evaluable
CE-EOT	Clinically Evaluable at End of Treatment
CE-LFU	Clinically Evaluable at Late Follow Up
CE-TOC	Clinically Evaluable at Test-of-Cure
CI	Confidence interval
DMC	Data Monitoring Committee
ECG	Electrocardiogram
ECR	Early Clinical Response
eCRF	Electronic case report form
EMA	European Medicines Agency
emicroITT	Expanded Microbiological Intent-to-Treat
EOT	End of Treatment
EU	European Union
F	Fahrenheit
FDA	US Food and Drug Administration
GGT	Gamma-glutamyl-transferase
IAC	Interim Analysis Committee
IACR	Investigator's Assessment of Clinical Response
IRT	Interactive response technology
ITT	Intent-to-Treat
IV	Intravenous
LFU	Late follow-up
LLN	Lower limit of normal
LPF	Low power field
ME	Microbiologically evaluable
MedDRA	Medical Dictionary for Regulatory Activities
ME-EOT	Microbiologically Evaluable at End of Treatment

ME-LFU	Microbiologically Evaluable at Late Follow Up
ME-TOC	Microbiologically Evaluable at Test-of-Cure
Mg	Milligram
MIC	Minimum inhibitory concentration
microITT	Microbiological Intent-to-Treat
microITT-2	Microbiological Intent-to-Treat-2
mITT	Modified Intent-to-Treat
mmHg	Millimeter of mercury
MRSA	Methicillin resistant Staphylococcus aureus
MSSA	Methicillin susceptible Staphylococcus aureus
NA	Not applicable
NI	Non-inferiority
PCS	Potentially clinically significant
PISP	Penicillin intermediate Streptococcus pneumoniae
PMNs	Polymorphonuclear neutrophils
PO	By mouth (oral)
PORT	Pneumonia Outcomes Research Team
PRO	Patient Reported Outcome
PRSP	Penicillin resistant Streptococcus pneumoniae
PSSP	Penicillin susceptible Streptococcus pneumoniae
PVL	Panton-Valentine Leukocidin
q12h	Every 12 hours
q24h	Every 24 hours
QTcF	QT interval corrected by the Fridericia formula
RQ-PCR	Real-time quantitative Polymerase chain reaction
SAE	Serious Adverse Event
SAP	Statistical Analysis Plan
SD	Standard deviation
SEC	Squamous epithelial cells
SIRS	Systemic Inflammatory Response Syndrome
Spp	Species
TEAE	Treatment-emergent adverse event
TOC	Test of Cure
UAT	Urinary antigen test
ULN	Upper limit of normal
US	United States
WBC	White blood cell
WHO	World Health Organization

## 1.0 INTRODUCTION

This statistical analysis plan (SAP) provides the framework for the summarization and analysis of the clinical data from the study, “A Phase 3, Randomized, Double-Blind, Double-Dummy Study to Compare the Efficacy and Safety of Oral Lefamulin (BC-3781) Versus Oral Moxifloxacin in Adults With Community-Acquired Bacterial Pneumonia”. Changes made to this SAP after it has been signed but prior to database lock will be documented in an amendment. Any important changes made to the analysis after database lock will be described in the clinical study report. Pharmacokinetic analyses (except for the description of plasma concentrations) and health utilization and patient-reported outcome analyses will not be included in this SAP. A separate analysis plan will be written for the health utilization and patient-reported outcome analyses.

Study NAB-BC-3781-3102 has been designed to address both the United States (US) Food and Drug Administration (FDA) and European Medicines Agency (EMA) regulatory requirements. While the EMA supports the assessment of clinical response by the Investigator at a Test of Cure (TOC) Visit (which is scheduled to occur 5-10 days after the last dose of study drug) as the primary endpoint, the FDA is using an earlier primary endpoint (3-5 days after the first dose of study drug) based on improvement in pneumonia symptoms.

This SAP addresses the primary efficacy outcome and analyses for the FDA. A SAP Addendum will be developed to address the different primary efficacy outcome and analyses for the EMA.

## 2.0 STUDY DESIGN

This is a Phase 3, multicenter, multinational, randomized, double-blind, double-dummy comparative efficacy and safety study of oral lefamulin (600 mg every 12 hours [q12h]) and oral moxifloxacin (400 mg every 24 hours [q24h]) in the treatment of adult subjects with community-acquired bacterial pneumonia (CABP). The duration of blinded study drug administration is 7 days. Subjects randomized to lefamulin will receive oral lefamulin 600 mg q12h for 5 days (10 doses) and oral moxifloxacin placebo q24h for 7 days (7 doses). Subjects randomized to moxifloxacin will receive oral moxifloxacin 400 mg q24h for 7 days (7 doses) and oral lefamulin placebo q12h for 5 days (10 doses).

A total of 738 subjects with CABP (Pneumonia Outcomes Research Team [PORT] Risk Class II, III, or IV) will be randomized 1:1 to study treatment (369 to each treatment arm) using interactive response technology (IRT). Randomization will be stratified by geographic region (US vs ex-US), prior single dose treatment with a short acting antibiotic vs. none, and by PORT risk class: (PORT II vs. III/IV). Enrollment of subjects receiving prior single dose treatment with a short acting antibiotic will be capped at 25%. A minimum of 50% of the total number of subjects randomized will have a PORT Risk Class of III or IV.

After informed consent is obtained, all potential study participants undergo screening evaluations, which includes a medical history, clinical assessments, and laboratory assessments. An assessment of Early Clinical Response (ECR) will occur  $96 \pm 24$  hours after the first dose of study drug. An Investigator’s Assessment of Clinical Response (IACR) will be evaluated at the End of Treatment (EOT) Visit (within 1 day after the last dose of study drug or if not logistically

feasible [eg, visit would need to be conducted over a weekend], then conducting the visit within 2 days is acceptable), at the TOC Visit (5 to 10 days after the last dose of study drug), and at a Late Follow-up (LFU) Visit conducted on Day 30 ( $\pm 3$  days).

The schedule of assessments and procedures is provided in [Appendix A](#).

### 3.0 STUDY OBJECTIVES

Primary:

Demonstrate the non-inferiority (NI) of lefamulin versus comparator with respect to the Early Clinical Response ( $96 \pm 24$  hours after the first dose of study drug) in the Intent-to-Treat (ITT) Analysis Set

Secondary:

- Demonstrate the NI of lefamulin versus comparator with respect to the Investigator's Assessment of Clinical Response at TOC (ie, 5-10 days after the last dose of study drug) in the modified-ITT (mITT) and Clinically Evaluable at TOC (CE-TOC) Analysis Sets.  
**NOTE:** This is the primary efficacy endpoint for the EMA.
- Evaluate the Early Clinical Response in the Microbiological Intent-to-Treat (microITT) Analysis Set.
- Evaluate the Investigator's Assessment of Clinical Response at TOC in the microITT and Microbiologically Evaluable at TOC (ME-TOC) Analysis Sets
- Evaluate the By-Pathogen Microbiologic Response at TOC in the microITT and ME-TOC Analysis Sets
- Evaluate the safety and tolerability of lefamulin versus comparator in the Safety Analysis Set
- Evaluate 28 day all-cause mortality in the ITT Analysis Set

Additional:

- Evaluate the Early Clinical Response by baseline pathogen in the microITT Analysis Set
- Evaluate the Investigator's Assessment of Clinical Response at EOT (ie, within 2 days after the last dose of study drug) and at LFU in the mITT and Clinically Evaluable (CE) Analysis Sets (CE-EOT for IACR at EOT and CE-LFU for IACR at LFU).
- Evaluate the Investigator's Assessment of Clinical Response by baseline pathogen at TOC and LFU in the microITT and Microbiologically Evaluable (ME) Analysis Sets (ME-TOC for IACR at TOC and ME-LFU for IACR at LFU).
- Evaluate the By-Subject Microbiologic Response at TOC in the microITT and ME-TOC Analysis Sets
- Evaluate the Early Clinical Response PLUS improvement in vital signs in the ITT Analysis Set

- Evaluate the plasma pharmacokinetics of lefamulin and its main metabolite, BC-8041, in the Pharmacokinetic Analysis Set
- Explore a variety of health utilization variables and an investigational patient reported outcome measure in subjects receiving lefamulin compared with subjects receiving comparator.

#### **4.0 PATHOGEN IDENTIFICATION**

All microbiology data will be reviewed by the Sponsor for pathogen identification. A pathogen is defined as bacteria implicated as causative in a subject's CABP and will be determined separately for each subject. Baseline pathogens and post-baseline pathogens will be identified.

Additional details regarding the pathogen review process and determination are included in the Evaluability Review Plan.

Baseline for microbiologic specimens is defined as the 24-hour period prior to the administration of the first dose of study drug and the 24 hours after the first dose of study drug. A pathogen identified from a respiratory (pleural fluid, bronchoalveolar lavage (BAL), sputum), blood for culture, urine, nasopharyngeal or oropharyngeal specimen collected at baseline is considered a baseline pathogen. An atypical pathogen identified by serology is considered a baseline pathogen if the baseline sample is collected in the 24-hour period prior to the administration of the first dose of study drug or the 24 hours after the first dose of study. A Gram stain from a specimen collected at baseline is considered a baseline Gram stain.

If more than 1 specimen is taken during the baseline period, all specimens will be reviewed for pathogen identification. If the same pathogen (based on genus and species) is identified from more than 1 specimen, the pathogen with the highest minimum inhibitory concentration (MIC) to study drug received will be considered the baseline pathogen. If the pathogens have the same MIC to study drug received, the one with the highest accession number will be considered the baseline pathogen.

Post-baseline is defined as the period starting 24 hours after the first dose of study drug. A pathogen identified from a specimen collected post-baseline is considered a post-baseline pathogen. Only pathogens identified by culture of the sputum, BAL, pleural fluid or blood are considered post-baseline pathogens.

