## 5.7 Microbiologically Evaluable (ME) Analysis Sets

The ME Analysis Sets (ME-EOT, ME-TOC and ME-LFU) will consist of all subjects who meet criteria for inclusion in both the microITT and the CE-EOT (ME-EOT) Analysis Set, the CE-TOC (ME-TOC) Analysis Set or the CE-LFU (ME-LFU) Analysis Set. Subjects who have CABP caused *only* by a pathogen(s) resistant to moxifloxacin or lefamulin will be excluded from the ME Analysis Sets. Resistance is defined as: 1) a pathogen resistant to moxifloxacin or non-susceptible to lefamulin based on susceptibility results from the central laboratory, or 2) a pathogen in the *Enterobacteriaceae* family or a non-fermenting Gram-negative pathogen (with the exception of *Legionella pneumophila* and *Moraxella catarrhalis*), unless susceptibility data from the central laboratory is available and indicates the pathogen is susceptible to both moxifloxacin (Table 9) and lefamulin (Table 10).

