### 8.3 Baseline Microbiological Assessments

Baseline pathogens will be summarized by genus and species, treatment group and overall for the microITT, microITT-2, emicroITT, and ME-TOC Analysis Sets. Selected pathogens will also be summarized by phenotypic susceptibility profile. In addition, for *Staphylococcus aureus* isolated at baseline, the PVL and MecA status (positive or negative) will be summarized. [Table 8](#) provides the definition for each pathogen susceptibility profile.

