Baseline pathogens will be summarized by treatment group and overall, by genus and species, and diagnostic modality for the microITT, microITT-2, and ME-TOC Analysis Sets. The number and percentage of subjects with specimens tested, by testing modality, and the number and percentage of subjects with specimens positive for a pathogen and the specific pathogen (genus and species) will be presented. The number and percentage of subjects with monomicrobial or polymicrobial gram-positive or gram-negative pathogen infections, only atypical pathogens, a mixture of gram-positive and gram-negative pathogens, a mixture of gram-positive and atypical pathogens, a mixture of gram-negative and atypical pathogens or a mixture of gram-positive, gram-negative and atypical pathogens will be summarized by treatment group and overall for the microITT, microITT-2 and ME-TOC Analysis Sets.

The MIC distribution detailing the number and percentage of pathogens at the respective MIC values and the cumulative distribution will be presented for lefamulin and moxifloxacin by baseline pathogen, phenotype and study drug for both treatment groups combined and by treatment group for subjects in the microITT and ME-TOC Analysis Sets. Disk diffusion zone diameters for lefamulin and moxifloxacin will be summarized by baseline pathogen, phenotype, and study drug for both treatment groups combined and by treatment group for subjects in the microITT and ME-TOC Analysis Sets. Scatter plots of the MIC to lefamulin versus the disk diffusion zone diameter will be provided for *Streptococcus pneumoniae*, *Haemophilus influenzae*, *Staphylococcus aureus*, and *Moraxella catarrhalis*, as long as there are at least 10 pathogens in the lefamulin group.

The minimum inhibitory concentration 50 (MIC50), 90 (MIC90), and range of lefamulin and moxifloxacin for baseline pathogens and susceptibility (susceptible and resistant, based on MIC and zone diameter) of pathogens to lefamulin and moxifloxacin will be summarized by baseline pathogen for both treatment groups combined and by treatment group for subjects in the microITT and ME-TOC Analysis Sets. MIC50 and MIC90 will be provided only where there are at least 10 pathogens of a particular species; range will be provided for all pathogens.

Baseline pathogens are considered susceptible (S), intermediate (I), or resistant (R) to moxifloxacin and S or non-susceptible (NS) to lefamulin according to the criteria in [Table 9](#) and [Table 10](#).

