### **8.5.3.4 By-Pathogen Microbiological Response at the TOC Visit in the microITT and ME-TOC Analysis Sets**

The proportion of subjects with a microbiological response of success by baseline pathogen (and where relevant, the susceptibility phenotype) at the TOC Visit will be tabulated separately by treatment group for subjects in the microITT and ME-TOC Analysis Sets. Distinct pathogens are based on genus and species and where relevant, the susceptibility phenotype as defined in [Table 8](#).

For all by-pathogen analyses, subjects with a pathogen of the same genus and species with more than 1 phenotype, for example both MRSA and MSSA, will be counted once for each phenotype and once for the overall tabulation of the pathogen, for example, *Staphylococcus aureus*.

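### SAP 4.0 selects the baseline isolate by MIC to the drug received, so section 8.3 baseline MIC and susceptibility tables depend on arm for subjects with discordant repeat isolates

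*SAP*

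**What the plan says.** SAP 4.0 sets the trigger: "If the same pathogen (based on genus and species) is identified from more than 1 specimen". In that case "the pathogen with the highest minimum inhibitory concentration (MIC) to study drug received will be considered the baseline pathogen". Ties are settled on the same drug: "If the pathogens have the same MIC to study drug received, the one with the highest accession number will be considered the baseline pathogen".

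SAP 8.3 uses the term baseline pathogen for tables that cover both drugs. The MIC distributions "will be presented for lefamulin and moxifloxacin by baseline pathogen, phenotype and study drug for both treatment groups combined and by treatment group", in the microITT and ME-TOC sets. Zone diameters, MIC50/90, range and susceptibility follow the same layout. The same section adds that "Selected pathogens will also be summarized by phenotypic susceptibility profile", with no rule for a subject who has two phenotypes of one species.

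Two other sections bear on the point. SAP 8.5.3.4, for all by-pathogen analyses, says that a subject with several phenotypes of one species "will be counted once for each phenotype and once for the overall tabulation of the pathogen". SAP 5.7 removes from the ME sets those subjects whose pneumonia is due solely to resistant pathogens. Its first definition of resistance is "a pathogen resistant to moxifloxacin or non-susceptible to lefamulin based on susceptibility results from the central laboratory", with no reference to the subject's own arm.

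**The concern.** A baseline table describes patients before treatment, so an identical patient should give the same entry in either arm. Under 4.0 the entry can differ, because the treatment received decides which isolate is tabulated. Each arm then shows its own drug's least favourable isolate. A difference between the arm columns could be read as a baseline imbalance in susceptibility when it comes only from the selection rule.

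The same definition could reach further. If the 5.7 exclusion were programmed from the one isolate that 4.0 labels the baseline pathogen, membership of ME-TOC would depend on arm. ME-TOC carries two of the SAP's secondary outcomes: investigator-assessed response and by-pathogen response at TOC.

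**Working it through.** The plan gives no figure for this rule, so there is nothing to reproduce. I applied the rule to example isolates and then sized it under stated assumptions.

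**1. Example pairs.** The MICs are hypothetical *S. pneumoniae* values in µg/mL, written (lefamulin, moxifloxacin). The breakpoints are from SAP Tables 9 and 10: lefamulin non-susceptible above 1, moxifloxacin resistant at 4 or more.

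| Isolates | Selected, lefamulin arm | Selected, moxifloxacin arm | ME if read from selected isolate | ME if read from all isolates |
|---|---|---|---|---|
| A (2, 0.12), B (0.25, 0.25) | A, lefamulin non-susceptible | B, susceptible to both | out / in | in / in |
| A (0.25, 4), B (0.5, 0.12) | B, susceptible to both | A, moxifloxacin resistant | in / out | in / in |
| A (0.12, 0.12), B (0.25, 0.25) | B | B | in / in | in / in |

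The ME columns give lefamulin arm / moxifloxacin arm and assume no other pathogen. In the first two rows the 8.3 entries depend on arm whichever ME reading is taken. In the second row the quinolone-resistant phenotype also appears in one arm only, unless every phenotype is counted. In the third row the ranking agrees on both drugs and nothing changes.

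**2. How often, and how far.** Assumptions, none from the documents: two isolates per affected subject; MICs to the two drugs independent; each MIC one doubling dilution up or down with probability q per direction; ties to the second isolate.

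- P(tie on one drug) = 2q² + (1 − 2q)². P(first isolate selected) = s = (1 − P(tie))/2.
- P(selection differs by arm) = 2s(1 − s).
- Mean log2 MIC to a drug is 2q(1 − q) when the isolate is selected on that drug and 0 when selected on the other.

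For q = 0.05, s = 0.0925, so P(differs) = 16.8% and the shift is 0.095 dilutions. For q = 0.10, s = 0.17, giving 28.2% and 0.18. For q = 0.25, s = 0.3125, giving 43.0% and 0.375.

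If 5% to 30% of subjects in a table have two isolates of the species (assumed):

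- subjects affected: 0.05 × 16.8% = 0.8% to 0.30 × 43.0% = 12.9%;
- mean shift: 0.05 × 0.095 = 0.005 to 0.30 × 0.375 = 0.11 dilutions.

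**3. Near a breakpoint.** Protocol 1.3 gives a lefamulin MIC90 of 2 µg/mL for *H. influenzae*, and SAP Table 10 sets susceptible at 2 or less, so at most about 10% of isolates exceed the breakpoint. Suppose a proportion p of single isolates is non-susceptible. In the lefamulin arm the selected isolate is non-susceptible if either isolate is. In the moxifloxacin arm the proportion stays p, if the two drugs' MICs are independent.

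- Two unrelated isolates: 1 − (1 − p)² = 19.0% against 10.0% for p = 0.10, and 9.8% against 5.0% for p = 0.05.
- Two isolates of one strain, simulated with strain SD 0.8 and assay SD 0.4 to 0.8 dilutions (assumed): 14.4% to 16.8% against 10.0%, and 7.5% to 8.8% against 5.0%.

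These percentages apply only to subjects with two cultured isolates. For an assumed 100 *H. influenzae* subjects per arm with 5% to 30% duplicates, the extra non-susceptible entries at p = 0.10 number 100 × 0.05 × 0.044 = 0.2 to 100 × 0.30 × 0.068 = 2.0.

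**The case against.** The strongest reply is that little rests on this. The 8.3 tables are descriptive, ME-TOC has an unadjusted interval with no non-inferiority rule (SAP 8.5.3.3), and duplicates should be uncommon. Protocol 6.15.1 takes one screening sputum and repeats it only if inadequate, and an inadequate sputum fails the Gram-stain criterion in SAP 4.1. BAL and pleural fluid are taken only if clinically indicated. *S. pneumoniae* gives duplicates more readily, because a nasopharyngeal culture also counts, but its lefamulin MIC90 of 0.25 lies two dilutions below the breakpoint of 1. All of this stands and keeps the point small. It does not make the 8.3 tables arm-neutral.

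Some stronger readings are tempting, and the documents do not support them.

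- *The ME sets preferentially lose each drug's resistant subjects from its own arm.* Section 5.7 counts resistance to either drug in both arms, removes only subjects with no other cause than resistant pathogens, and does not say that it is read from the selected isolate. For *H. influenzae*, Table 9 has no moxifloxacin-resistant category, so a mirror-image loss cannot be shown there.
- *Phenotypes depend on arm throughout.* Section 8.5.3.4 prevents this in by-pathogen analyses. Only the baseline phenotype table is open.
- *A nasopharyngeal isolate displaces the blood isolate.* SAP 6.2.3 uses blood and respiratory cultures together for outcome, 8.5.4.1 analyses blood pathogens separately, and 8.3 tabulates by diagnostic modality. No specimen hierarchy is needed.
- *The rule fails for undosed subjects.* It is undefined for them, but SAP 7.1 expects under 1%, and the 48-hour criterion in 5.6 generally keeps them out of ME.
- *ME cannot be settled while blinded.* That follows only under the selected-isolate reading. The Evaluability Review Plan, which may address it, is not among the documents.

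**Conclusion.** The point holds for the section 8.3 tables. As written, the baseline MIC, MIC50/90, zone and susceptibility tables depend on treatment arm for subjects who have the same species cultured from more than one baseline specimen and whose isolates rank differently on the two drugs. A tie on one drug, broken by accession number, can have the same effect. The combined column mixes two selection rules, and the baseline phenotype table may share the problem. For ME membership the finding is an ambiguity to close, not a stated consequence.

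The size is unknown, because the documents give neither the share of subjects with repeat isolates nor how far such isolates disagree. The ranges above rest on assumed duplicates, variances and independence between drugs, and the effect is probably small. ITT, mITT, CE and microITT membership, the primary ECR analysis and power do not use the selected isolate and are unaffected. The rule remains a coherent choice where outcome is tabulated against the MIC to the subject's own drug.

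**What to change.** Amend the SAP before unblinding:

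- **4.0:** restrict selection by MIC to the drug received to the outcome-by-MIC and outcome-by-zone tables and to decreasing susceptibility (6.4).
- **8.3:** for tables of MIC, zone or susceptibility to a given drug, use one treatment-independent rule in both arms. An example is the highest MIC to that drug among the subject's baseline isolates of the species. This also covers undosed microITT subjects.
- **5.7:** state that resistance is judged on all baseline isolates, identically in both arms, so that a subject with any isolate susceptible to both drugs is not excluded. Applying each criterion to the highest MIC for each drug would not serve here, because it would exclude subjects who do have such an isolate. Judged on all isolates, this criterion can be settled while blinded.
- **8.3 phenotype table:** apply the count-every-phenotype rule of 8.5.3.4, and reconcile 4.0 with it.

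The cost is a few sentences and minor programming, with no new data. The between-arm artefact becomes zero by construction. Compared with the selected-isolate reading, a few subjects may stay in ME who would otherwise leave.
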